4.5 Screening

Medical history of each subject will be reviewed, and inclusion/exclusion criteria verified. Discontinuation of any concomitant medications or pretreatment instructions as determined by the investigator will be discussed. Pre and Post-Treatment instructions will be reviewed with the subject prior to signing the informed consent. Subjects will be asked questions about their medical history and may have a limited physical exam (no pelvic or and rectal exam will be performed).

Procedure for the Limited Physical Exam:

If the investigator determines that a limited physical is necessary, the exam will be similar to that of a basic annual physical exam performed by a primary care doctor to determine general overall health. The limited medical exam may include all or any of the following; vital signs such as blood pressure, heart rate, respiratory rate and body temperature, general appearance, listening to the heart, lungs and abdomen with a stethoscope, head and neck exam such as looking at the throat, tonsils, teeth, ears, eyes and nose and neurological exam such as testing muscle strength, reflexes, balance, sensory changes of the extremities and mental state.

4.6 Informed Consent Process and Enrollment

Subjects meeting the subject selection criteria for the study will sign the informed consent form and be assigned a subject identification number. Subjects will be de-identified through their subject identification number, which will be stored in a secure location. Subject identification numbers will be generated chronologically and assigned only to subjects who have met all the study selection criteria and have signed the informed consent form. The informed consent will be obtained prior to a subject's involvement in any study related procedures. Non-English speaking individuals cannot be enrolled in this study. Employees of the sponsor or the Investigator may be enrolled in this study. A subject will be considered enrolled in the study once they have signed the informed consent form.

4.7 Pretreatment

- Photographs, OCT, and Ultrasound measurements may be taken pretreatment.
- If the subject is of childbearing potential (i.e. females not post-menopausal or not surgically sterile) they will be asked if they are pregnant and the date of their last menstrual cycle. A urine or serum pregnancy test may be conducted at the Investigators discretion at any time. If the treatment area is on the abdomen, then urine or serum pregnancy test will be conducted. If a urine or serum pregnancy test is conducted, then a negative result must be obtained within 24 hours prior to the procedure.
- A treatment area will be identified by the investigator. Subjects may receive facial treatments or isolated areas of treatment on other areas of the body
- A marker may be used to define the area.

- Standard pre-treatment instructions will be reviewed, and the subject will be instructed to adhere to the following:
 - Do not receive other treatments within the study area for the duration of the study.
 - If treatment is on the face;
 1. Do not apply any products or makeup to general eye area for 12 hours (or more) prior to each study visit.
 2. Remove makeup and wash facial area prior to treatment.
 - Please remove all makeup, and any lotions or sun block from the treatment area. Any preparations left on the skin will act as impedance to the energy and will diminish the effects.
 - The treatment area must be free of any open lesions or infections.
 - For an optimum treatment, hydrate by drinking water or hydrating fluids several days in preparation. Avoid alcohol if possible. The same procedure should be followed prior to each visit.

4.8 Treatment

- Radiofrequency Device Treatment:
 - The type of treatment will determine if gel should be applied to the skin prior to treatment. The gel is a conductive gel created for treatments that use radio frequency (RF) to ensure the proper connection between the hand piece and the skin.
 - A neutral pad will be used in accordance with the operator's manual for the device.
 - The hand piece, applicator or tip will be placed in contact with the skin.
 - The entire defined treatment area will then be treated by delivering energy to the skin.
 - The hand piece, number of passes and parameters used for the treatment will be determined by the Investigator.
 - Parameters may be adjusted throughout the treatment to increase subject comfort.
 - Contact cooling built into the 60mm handpiece may be used to increase subject comfort.
 - Nitronox may be used to increase subject comfort and will be determined by the Investigator.
- Procedural adverse events will be documented.
- Subjects will be asked to report the general level of treatment discomfort/pain on a scale of 0 (none) to 10 (maximum intolerable pain).
- Some subjects may have an incomplete response or no response by the end of the study. At the end of the study treatments using an FDA approved/cleared treatment method may be discussed with the subject and obtained at the cost of the subject.

4.9 Post-Treatment

- Photographs may be taken post treatment.
- Standard post-treatment care instructions will be reviewed and may be instructed to adhere to the following:
 - Wash skin with tepid water and a gentle cleanser.
 - If the skin is slightly pink or red in areas following the treatment, avoid hot water when washing or showering until any erythema (redness) has subsided.

- Makeup (preferably mineral-based) is not encouraged but may be applied immediately post-treatment.
- Soothing creams or moisturizers may be used.
- If the treatment area may be exposed to the sun; use a sun block with an SPF of 30 or greater to help prevent sun damage. This treatment does not cause photosensitivity.
- Subjects may be given a diary to assess recovery time to be completed during the week post the treatment.
- Subjects and clinicians may be asked to complete a treatment experience questionnaire.

4.10 Follow Up

- Subjects will receive a phone call or attend a visit 2 days and/or 1-week post treatment to record side effects. If a side effect is tracked, the site will continue to call the subject until the event resolves. If deemed necessary by the investigator, the subject may attend an unscheduled visit for side effect assessment.
- The subject may return for a follow up visit at 30, 90 and 180 days post last treatment for side effect and efficacy assessments.
- The assessments listed in the schedule of activities and observations table (Section 4.13) will be performed at all follow up visits.
- Adverse events will be assessed at all follow up visits.

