4.0 PROTOCOL

4.1 Purpose and Objectives

The purpose of this study is to develop parameters and assess the safety of the radiofrequency device for a variety of treatments. Treatment results may also be evaluated.

The Primary Objectives are:

- To develop treatment parameters.
- Assess the safety through recording of side effects during course of study.

The Secondary Objectives are:

- Subject satisfaction via continuous verbal feedback during the procedure and at follow up visits.
- Assess the ease of use, patient response, treatment time, functions of the new device.

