4.2 Protocol Summary

Subjects are to be enrolled in this clinical study if they are 18 years of age or older. Up to 225 subjects will be enrolled at 8 study centers. All subjects may receive up to 10 treatments or multiple treatment areas. Subjects will receive a phone call or attend a visit at 2 days and/or 1 week post treatment to record side effects. If a side effect is tracked, the site will continue to call the subject until the event resolves. If deemed necessary by the investigator, the subject may attend an unscheduled visit for side effect assessment. The subject may return for optional follow up visits at 30, 90 and 180 days post last treatment for side effect and efficacy assessments.

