4.13 Schedule of Activities and Observations

Procedure	Screening/ Pretreatment*	Visit 1-5: Treatment Visits	Visit 6: (optional) 2 Day Post Last Treatment Visit or Phone Call	Visit 7: 1 Week Post Treatment Visit or Phone Call	Visit 8: (optional) 30 Day Post Last Treatment Visit	Visit 9: (optional) 90 Day Post Last Treatment Visit	Visit 10: (optional) 180 Day Post Last Treatment Visit
Medical History	X						
Pregnancy Verification	X						
Informed Consent	X						
Treatment Discomfort/ Pain Evaluation		X					
Treatment		X					
Photographs	X	X	X	X	X	X	X
Subject Experience		X					
User Experience		X					
Diary***		X		X			
OCT***	X	X		X	X	X	
Ultrasound***	X	X		X	X	X	
Subject Satisfaction					X	X	X
Adverse Events Assessment **		X	X	X	X	X	X

* Screening/Pretreatment activities must be performed within 30 days prior to 1st treatment and may be performed on the same day as Visit 1.

** If deemed necessary by the investigator, the subject may attend an unscheduled visit for side effect assessment.

***Ultrasound (US), Optical Coherence Tomography (OCT), and the Diary are optional assessments.

The sponsor anticipates that all subjects can be enrolled within 6 months. The subject participation in this study will last approximately to 1-7 months. The total duration of this study is anticipated to last approximately two years.

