9.0 ADVERSE REACTIONS DEFINITIONS AND REPORTING REQUIREMENTS

All adverse events that occur, starting from the time of the first treatment, will be recorded in the source documents.

Adverse Events occurring will be captured and followed until the condition resolves, stabilizes, is otherwise explained, or the subject is lost to follow-up. Subjects will be instructed that they may contact the Investigator at any time throughout the course of the study.

The Investigator and/or designated study staff will review each event and assess its relationship to the study device (not related, unlikely, possible, probable, and highly probable). The following definitions will be used for rating relationship to the device treatments:

- Not related – The event is clearly related to other factors such as the subject’s clinical state, therapeutic interventions, or concomitant medications administered to the subject.
- Unlikely – The event was most likely produced by other factors such as the subject’s clinical state, therapeutic interventions, or a concomitant medication administered to the subject; and does not follow a known response pattern to the investigational product.
- Possible – The event follows a reasonable temporal sequence from the time of investigational product administration; **and/or** follows a known response pattern to the study sampling sessions; **but** could have been produced by other factors such as the subject’s clinical state, therapeutic interventions, or concomitant medications administered to the subject.
- Probable – The event follows a reasonable temporal sequence from the time of investigational product administration; **and** follows a known response pattern to the investigational product; **and** cannot be reasonably explained by other factors such as the subject’s clinical state, therapeutic interventions, or concomitant medications administered to the subject.

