10.0 PROTOCOL DEVIATIONS

All requests for protocol deviations by the Investigator have to be communicated to the sponsor in writing and if accepted by the Sponsor must be approved by the IRB. If a deviation occurs, the Investigator must inform the Sponsor as soon as possible. The Sponsor will notify the IRB in accordance with IRB specific policies.

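### Sections 4.2 and 4.10 let a day-2 contact stand alone while Section 4.13 implies a required 1-week contact, so side effects starting between about day 2 and day 7 after the last treatment may not be sought alike in all subjects

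*Combined protocol and SAP*

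**What the plan says.** Three sections of the combined protocol and SAP set the early side-effect contact.

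- Section 4.2 (Protocol Summary): "Subjects will receive a phone call or attend a visit at 2 days and/or 1 week post treatment to record side effects".
- Section 4.10 (Follow Up): "Subjects will receive a phone call or attend a visit 2 days and/or 1-week post treatment to record side effects".
- Section 4.13 (Schedule of Activities and Observations) has one column headed "Visit 6: (optional) 2 Day Post Last Treatment Visit or Phone Call" and the next headed "Visit 7: 1 Week Post Treatment Visit or Phone Call". Adverse event assessment is marked in both.

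For later follow-up, Section 4.2 says "The subject may return for optional follow up visits at 30, 90 and 180 days post last treatment", and Section 4.13 labels those three visits optional as well.

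Section 4.1 makes this a primary matter: "Assess the safety through recording of side effects during course of study".

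**The concern.** The rule for the last scheduled safety contact depends on which section a site reads. Under the text of 4.2 and 4.10, a site may call at day 2, hear of nothing, and have no further scheduled contact with that subject. Under 4.13 the same site would be expected to ask again at 1 week.

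Two things are at stake. The first is equal ascertainment. Up to 8 centers may apply the rule differently, and an effect that starts after the day-2 contact would be actively sought in some subjects and depend on the subject coming forward in others. Section 4.16 lists anticipated effects such as infection, prolonged swelling, hardness and nodules without onset times, so the text gives no ground for treating day 2 as late enough. The second is deviation status. Section 10.0 says "If a deviation occurs, the Investigator must inform the Sponsor as soon as possible", but whether a subject contacted only at day 2 is a deviation depends on the section applied.

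**Working it through.** The plan states no figure on this point, so the check is a comparison of the texts.

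**Step 1: which contact patterns comply.**

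| Contacts made | Sections 4.2 and 4.10 | Section 4.13 |
|---|---|---|
| Day 2 and 1 week | complies | complies |
| 1 week only | complies | complies |
| Day 2 only | complies | misses Visit 7 |
| Neither | does not comply | does not comply |

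The sections disagree on one pattern, day 2 only. That Visit 7 is required is an inference from the labels: of the five follow-up columns, Visits 6, 8, 9 and 10 are marked optional and Visit 7 is not.

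**Step 2: does any text settle it?** Section 4.10 refers to 4.13 for the assessments to be done at follow-up visits. It does not refer to 4.13 for which visits must take place. No section says which text prevails.

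**Step 3: what could close the gap for a day-2-only subject?**

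- Calls until resolution (4.2, 4.10) start only once a side effect has been recorded.
- Treatment visits carry an adverse event assessment (4.13), and Section 4.15 calls for recording at all visits. They can pick up late effects of every treatment except the last.
- The 30-, 90- and 180-day visits are optional.
- The 7-day diary (4.9, 4.14) is optional.
- Unscheduled visits (4.11) and contact started by the subject (9.0) require someone to raise the matter.

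What remains is a subject with nothing recorded at day 2 after the last or only treatment and no later visit.

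**Step 4: which effects are affected.** The 1-week contact can find only what has started by about day 7. An effect that starts later is missed by that contact under either rule. The difference between the rules is therefore confined to onset between about day 2 and day 7.

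**Step 5: size.** Let *d* be the share of subjects with day-2 contact only and no later visit, and *u* the share of affected subjects among them whose effect still becomes known through self-report or diary. Suppose the 1-week contact finds every effect with onset in that window, and onset does not depend on the contact pattern. The fraction of such effects left unrecorded is then *d* × (1 − *u*). The documents give neither *d* nor *u*, nor any rate of effects starting in the window. Purely assumed values show how it scales:

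- *d* = 0: 0
- *d* = 0.1, *u* = 0.5: 0.1 × 0.5 = 0.05
- *d* = 0.3, *u* = 0: 0.3 × 1 = 0.30
- *d* = 0.5, *u* = 0: 0.5 × 1 = 0.50

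A range from nothing to half is not an estimate. It shows that the result rests on a practice the documents do not describe.

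**The case against.** The strongest reply is that the sections can be read together. Contact at 1 week, with or without day 2, satisfies all three, so a site that works from the schedule is never in conflict. Nothing shows that any site uses the looser wording to skip Visit 7. The protocol also has other safeguards, including in Section 9.0: "Subjects will be instructed that they may contact the Investigator at any time throughout the course of the study". On this view the matter is editorial.

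Much of that stands. The conflict is narrow, harm arises only where a site relies on day 2 alone, and the safeguards reduce the loss. They do not make ascertainment equal, because after the last treatment they depend on the subject or on an optional element. The looser rule also appears twice, in the summary and in the follow-up section, where a site would look for it.

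A reader might infer three stronger things that the documents do not support.

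- *That safety follow-up can end at day 2 after every treatment.* It cannot where another treatment visit follows, because adverse events are assessed there.
- *That a definite number of side effects will be missed.* That would need assumed shares throughout and would take the limit of 225 as the number enrolled. It would also have to avoid crediting the 1-week call with effects that start after day 7. In addition, Appendix A dates the 2- and 7-day follow-up to October 2018, so an unknown number of earlier subjects may have finished under other rules.
- *That the schedule's five treatment visits, set against up to 10 treatments in 4.2, are part of the same fault.* That is a separate clerical alignment, and this point does not need it.

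**Conclusion.** The inconsistency is in the operative text and holds in a limited form. Sections 4.2 and 4.10 permit day-2 contact alone; Section 4.13, read by its labels, does not. The consequence is confined to effects that start between about day 2 and day 7 after the last or only treatment, in subjects with no later visit. There it makes a primary safety outcome depend partly on which section a site followed.

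The conclusion rests on reading the unmarked Visit 7 as required, and on some sites using the looser rule. The first is the natural reading but is nowhere stated; the second is unknown. The size cannot be estimated from the documents. If few subjects have day-2 contact only, it is near zero. This is a minor point, worth correcting because the remedy is cheap.

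A related ambiguity should be settled with it. The 1-week column omits the word *last*, which the 2-, 30-, 90- and 180-day columns include, and 4.2 and 4.10 omit it for both early contacts. It is therefore unclear whether the 1-week contact follows each treatment or only the final one.

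**What to change.** Make three changes together.

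1. In Sections 4.2 and 4.10, replace the *and/or* rule with: *A phone call or visit 1 week after the last treatment is required; a 2-day contact is an optional addition.*
2. In Section 4.13, relabel Visit 7 so that it is timed from the last treatment and marked as required.
3. State that side effects of earlier treatments are asked about at the next treatment visit. This settles the each-or-last question instead of leaving existing contacts undefined.

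The cost is one protocol amendment with written IRB approval (Section 20.0) and at most one extra call for each subject who would otherwise have had day-2 contact only. Section 4.13 already schedules that call.

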4.11 Unscheduled Visits

An unscheduled visit may be performed at any time during the study at the subject's request or as deemed necessary by the site Investigator. The date and reason for the unscheduled visit will be recorded in the source documentation.

4.12 Replacement of Subjects

Replacement of subjects who have withdrawn or been withdrawn from the study will be allowed to be replaced with prior approval from the sponsor and/or IRB.

4.13 Schedule of Activities and Observations

Procedure	Screening/ Pretreatment*	Visit 1-5: Treatment Visits	Visit 6: (optional) 2 Day Post Last Treatment Visit or Phone Call	Visit 7: 1 Week Post Treatment Visit or Phone Call	Visit 8: (optional) 30 Day Post Last Treatment Visit	Visit 9: (optional) 90 Day Post Last Treatment Visit	Visit 10: (optional) 180 Day Post Last Treatment Visit
Medical History	X						
Pregnancy Verification	X						
Informed Consent	X						
Treatment Discomfort/ Pain Evaluation		X					
Treatment		X					
Photographs	X	X	X	X	X	X	X
Subject Experience		X					
User Experience		X					
Diary***		X		X			
OCT***	X	X		X	X	X	
Ultrasound***	X	X		X	X	X	
Subject Satisfaction					X	X	X
Adverse Events Assessment **		X	X	X	X	X	X

* Screening/Pretreatment activities must be performed within 30 days prior to 1st treatment and may be performed on the same day as Visit 1.

** If deemed necessary by the investigator, the subject may attend an unscheduled visit for side effect assessment.

***Ultrasound (US), Optical Coherence Tomography (OCT), and the Diary are optional assessments.

The sponsor anticipates that all subjects can be enrolled within 6 months. The subject participation in this study will last approximately to 1-7 months. The total duration of this study is anticipated to last approximately two years.

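### The Section 4.13 schedule covers 5 of the 10 treatments that Section 4.2 permits, and it marks pregnancy verification only once, before the first

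*Combined protocol and SAP*

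**What the plan says.** **Number of treatments.** Section 4.2 states: "All subjects may receive up to 10 treatments or multiple treatment areas". The schedule in Section 4.13 has one treatment column, headed "Visit 1-5: Treatment Visits". Visits 6 to 10 are follow-up contacts and carry no treatment mark.

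**Pregnancy.** The schedule marks pregnancy verification once, in the Screening/Pretreatment column. Its footnote reads: "Screening/Pretreatment activities must be performed within 30 days prior to 1st treatment", and allows these activities on the day of Visit 1. Section 4.7 describes the check as two questions, on current pregnancy and on the last menstrual cycle. A test is compulsory when the treatment area is the abdomen and otherwise optional at any time. When a test is done, it must be negative within the 24 hours before the procedure. Pregnancy is an exclusion (4.4) and leads to removal from the study (5.0).

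**Early safety contact.** Section 4.10 says: "Subjects will receive a phone call or attend a visit 2 days and/or 1-week post treatment to record side effects", and Section 4.2 says much the same. For the later visits, Section 4.2 uses a different anchor: "The subject may return for optional follow up visits at 30, 90 and 180 days post last treatment". In the schedule the early contacts are headed "Visit 6: (optional) 2 Day Post Last Treatment Visit or Phone Call" and "Visit 7: 1 Week Post Treatment Visit or Phone Call".

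**The concern.** The schedule is the page that sites work from, and Section 4.10 makes it operative by requiring its listed assessments at follow-up visits. A site that follows it as drawn has no column for treatments 6 to 10. It may also treat a subject of childbearing potential repeatedly with no scheduled pregnancy re-check. Detection would then rest on the contraception requirement in 4.4, discretionary testing under 4.7 and the subject's own report under 5.0.

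The early contact is a lesser matter. Safety, through recording of side effects, is a primary objective (4.1). If some of the 8 centers ask about side effects a week after every treatment and others only after the last, ascertainment after the earlier treatments is not comparable between sites. This would matter mainly for longer-lasting effects such as burns, crusting, infection or nodules. Section 4.16 expects mild swelling and redness to clear within 2 to 24 hours.

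**Working it through.** The plan gives no figure to reproduce here. The check compares sections and counts.

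**Inputs from the protocol:** maximum treatments 10 (4.2); treatment visits 5 (4.13); screening 0 to 30 days before the first treatment (4.13); participation about 1 to 7 months (4.13); enrollment cap 225 (4.2).

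**Assumptions:** one treatment per visit; treatment gaps of 7, 14 or 30 days, because the protocol states no interval.

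**1. Treatments without a column.** 10 − 5 = 5, that is, treatments 6 to 10. Fitting 10 treatments into 5 visits would take two per visit, which no section describes.

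**2. Treatments without a scheduled pregnancy check.** 5 − 1 = 4 of 5 scheduled; 10 − 1 = 9 of 10 permitted. These count marks in the table. They become treatments with no *required* re-check only for non-abdominal areas and subjects of childbearing potential. Where 4.7 wants a step repeated it says so: the instructions on eye-area products and on hydration refer to each visit. The pregnancy questions carry no such wording.

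**3. Age of the last scheduled pregnancy questions at treatment n.** Age = (n − 1) × gap, plus 0 to 30 days for screening.

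| Gap | Treatment 5 | Treatment 10 |
|---|---|---|
| 7 days | 28 to 58 days | 63 to 93 days |
| 14 days | 56 to 86 days | 126 to 156 days |
| 30 days | 120 to 150 days | not feasible |

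The last cell is ruled out by the protocol's own duration. Seven months is about 213 days, and nine 30-day gaps take 9 × 30 = 270 days. With same-day screening and a 1-week contact at the end, the largest mean gap for ten treatments is (213 − 7)/9, or about 23 days.

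A subject who attends the optional 180-day visit has about 213 − 180 = 33 days for all treatments. The mean gap is then at most 33/4, about 8 days, for five treatments, and 33/9, under 4 days, for ten. The treatment-10 figures in the table therefore apply to subjects who skip that visit.

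**4. Early contact.** The 2-day heading contains the word *last*; Sections 4.2 and 4.10 do not use it for this contact. That is the only explicit conflict. The 1-week heading omits *last* and so matches the text, but it is a single column numbered after all treatment visits.

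The each-treatment and last-only readings differ by 225 × (5 − 1) = 900 contacts at five treatments per subject, and by 225 × (10 − 1) = 2,025 at ten. Under the last-only reading, side effects of an earlier treatment are first asked about at the next treatment visit. Relative to a 1-week contact, the delay is gap − 7: 0, 7 or 23 days for gaps of 7, 14 or 30 days.

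**The case against.** The strongest reply is that this is a clerical lag with several safeguards around it. The revision log (Appendix A) records an increase from 5 to 10 treatments, so the column label was probably just not updated. Section 4.2 also mentions multiple treatment areas and never defines whether several areas in one visit count as several treatments. On pregnancy, 4.7 is not limited to the first treatment and its 24-hour rule attaches to the procedure. Contraception is required, planned pregnancy is excluded, testing is allowed at any time, and suspected pregnancy must be reported at once. The sponsor classes the study as non-significant risk, and the protocol documents no fetal hazard from non-abdominal treatment. On side effects, events are recorded at all visits (4.15) and during procedures (4.8), and an optional diary covers the following 7 days. Once an event is known, "If a side effect is tracked, the site will continue to call the subject until the event resolves".

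Most of this stands and limits the point. It does not remove the mismatch between 4.2 and 4.13, nor supply a required repeat of the questions for non-abdominal areas.

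Four stronger inferences are tempting, and the documents do not support them:

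- *Pregnancy answers could be 270 to 300 days old.* That needs 30-day gaps over ten treatments, which exceeds the stated participation time.
- *Nine of ten treatments lack any pregnancy safeguard.* Abdominal treatments are arguably tested each time, and the count concerns only subjects of childbearing potential, whose number is not given.
- *Up to 2,025 safety contacts are lost.* The 900 and 2,025 figures are differences between two readings if all 225 subjects receive every treatment. The wording of 4.2 and 4.10 favors contact after each treatment, and weekly treatment loses nothing.
- *Side effects of treatments 6 to 10 go unrecorded.* Sections 4.8 and 4.15 apply to those treatments too.

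**Conclusion.** The point holds on its first two parts. Sections 4.2 and 4.13 conflict in the current text: at one treatment per visit, 5 of 10 permitted treatments have no scheduled visit. For non-abdominal areas in subjects of childbearing potential, up to 4 of 5 scheduled or 9 of 10 permitted treatments have no required pregnancy re-check. With assumed gaps of 7 to 14 days and the 180-day visit not attended, the last answers would be 63 to 156 days old at treatment 10.

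The third part is smaller. The explicit conflict concerns only the optional 2-day contact; the 1-week contact is unclear in timing, not contradictory.

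The analysis is chiefly descriptive, and no endpoint, sample size or error rate changes. This is a cheap improvement to participant protection and to the consistency of safety data, between minor and should-fix in weight. Confidence is high on the treatment-column mismatch and more moderate on the other two parts, which depend on how 4.7 and the 1-week column are read.

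**What to change.** Make one IRB-approved amendment:

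- Relabel the schedule column *Treatment Visits 1-10* and renumber the follow-up visits.
- Mark pregnancy verification, meaning the two Section 4.7 questions, at every treatment visit. State that each abdominal treatment needs a negative test within the preceding 24 hours.
- State in 4.2, 4.10 and 4.13 that the 1-week safety contact follows each treatment, that a treatment visit within 7 days counts as that contact, and that the 2-day contact is optional.

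The cost is an edit to the table and a sentence each in 4.2 and 4.10. Subjects of childbearing potential answer two questions per treatment visit. Repeat tests before abdominal treatments are arguably already required. The added calls are at most 9 per subject with ten treatments and 4 per subject with five. There are none where sites already call after each treatment or the next treatment falls within 7 days.
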